# **PASS** information

Title	A cross-sectional study to evaluate the effectiveness of additional Risk Minimisation Measures: A Survey among surgeons to assess their knowledge and understanding of selected risks of InductOs (dibotermin alfa/ACS) in Europe					
Protocol version identifier	2.0					
Date of last version of protocol	Not applicable					
EU PAS register number	EUPAS32916					
Active substance	M05BC01 Dibotermin Alfa					
Medicinal product	InductOs					
Product reference	EU/1/02/226/001-002					
Procedure number	EMEA/H/C/000408					
Marketing authorisation holder(s)	Medtronic BioPharma B.V.					
Joint PASS	No					
Research question and objectives	Primary questions:  Do physicians administering InductOs understand the potential for heterotopic ossification occurrence after spinal interbody fusion?  Do physicians administering InductOs know the appropriate measures to be taken to minimize the risk of heterotopic ossification occurrence?  Secondary question:  Was the knowledge on the risk of heterotopic ossification and minimization measures obtained from the SmPC, educational materials, professional training and literature, or a combination of these?					
Country(-ies) of study	France, Germany, Ireland, United Kingdom					
Author	[name], MSc [contact]					

# 2. List of abbreviations

ACS Absorbable Collagen Sponge

AE Adverse Event

ALIF Anterior Lumbar Interbody Fusion

ANSM Agence Nationale de Securité du Médicament et des produits de santé

aRMM Additional Risk Minimisation Measures

ATC Antomical Therapeutic Chemical

BfARM Bundesinstitut für Arzneimittel und Medizinprodukte

CA Competent Authority
CI Confidence Interval

DALYs Disability Adjusted Life Years EMA/EMEA European Medicine Agency

ENCePP European Network of Centers for Pharmacoepidemiology and

Pharmacovigilance

EU European Union

EU PAS European Post Approval Study
GDPR General Data Protection Regulations
GVP Good Pharmacovigilance Practices
HPRA Health Products Regulatory Authority
HROOL Health-Related Quality of Health

ICD International Classification of Diseases

MAH Marketing Authorisation Holder

MedDRA Medical Dictionary for Regulatory Activities

mg milligram

MHRA Medicines and Healthcare products Regulatory Agency

MSc Master of Science

OLIF Oblique Lateral Interbody Fusion

PAS Post Approval Study

PASS Post Approval Safety Study
PIR Product Information Report

PLIF Posterior Lumbar Interbody Fusion

PLF Posterior Lumbar Fusion

PRAC Pharmacovigilance Risk Assessment Committee

QALYs Quality Adjusted Life Years

rhBMP-2 Recombinant human Bone Morphogenetic Protein-2

RMP Risk Management Plan

SmPC Summary of Product Characteristics

TLIF Transforaminal Lumbar Interbody Fusion
WHO Drug Dictionary World Health Organisation Drug Dictionary

XLIF Extreme Lateral Interbody Fusion

## 4. Abstract

#### 4.1 Title

A cross-sectional study to evaluate the effectiveness of additional Risk Minimisation Measures: A Survey among surgeons to assess their knowledge and understanding of selected risks of InductOs (dibotermin alfa/ACS) in Europe.

Version 2.0; May 2020

[name], MSc, Medtronic BioPharma B.V.

# 4.2 Rationale and background

The active ingredient of InductOs is dibotermin alfa or recombinant human Bone Morphogenetic Protein 2. Its osteoinductive properties result in the induction of new bone tissue at the site of implantation.

InductOs is approved for:

- single-level lumbar interbody spine fusion as a substitute for autogenous bone graft in adults with degenerative disc disease who have had at least 6 months of non-operative treatment for this condition.
- treatment of acute tibia fractures in adults, as an adjunct to standard care using open fracture reduction and intramedullary unreamed nail fixation.

Additional risk minimisation measures (aRMM) to increase awareness about the identified risk of heterotopic ossification (especially in posterior surgical approaches for lumbar interbody fusion) and the potential risk of medication errors and misuse are available in the form of educational materials. This study is set up to measure the effectiveness of InductOs educational materials.

# 4.3 Research question and objectives

Primary questions:

- Do physicians administering InductOs understand the potential for heterotopic ossification occurrence after spinal interbody fusion?
- Do physicians administering InductOs know the appropriate measures to be taken to minimize the risk of heterotopic ossification occurrence?

#### Secondary question:

• Was the knowledge on the risk of heterotopic ossification and minimization measures obtained from the SmPC, educational materials, professional training and literature, or a combination of these?

## Objective:

The goal of this study is to assess the awareness of InductOs-using spine surgeons concerning heterotopic ossification in relation to the InductOs Risk Management Plan. A supplementary goal of this study is to gauge the clinician's awareness about the development of heterotopic ossification and the risk minimisation measures; specifically identifying from which source was any knowledge obtained.

## 4.4 Study design

An anonymous, cross sectional and non-interventional (online) survey of a sample of physicians from Germany, France, Ireland and the United Kingdom who have implanted InductOs in the last 2 years.

# 4.5 Population

#### Inclusion criteria

Participants of this study must meet the following inclusion criteria to be eligible to participate in this study:

1. Physicians that have implanted InductOs in a lumbar interbody spine fusion procedure at least once in the 24 months prior to taking this survey

#### Exclusion criteria

Participants meeting any of the following criteria will not be included in the study:

- 1. Physicians that participated in the testing of this survey, if there are substantial changes made to the survey post-pilot i.e. changes which, in the view of the research team, make the participants contributions invalid or potentially compromising of the study objectives.
- 2. Physicians that either themselves work for or have immediate family members who work for Medtronic, third parties involved in this study, or a regulatory agency (EMA, MHRA, HPRA, ANSM, BfARM).

#### 4.6 Variables

Information is collected on three main categories. The first category is used to describe the population and includes variables around demographics, type of practice, and level of experience in using InductOs. The second category of variables is aimed at measuring the awareness on the risk of heterotopic ossification, the educational materials and knowledge about safe use of InductOs presented in the educational materials. The third set of variables covers the different sources where information on the key messages in the educational materials could have been obtained.

#### 4.7 Data sources

Data will be collected using a standardized online questionnaire that has been translated into the local languages of the countries where the survey is being conducted.

## 4.8 Study size

The minimum sample size needed to obtain a proportion with confidence interval with the lower limit above the 80 % minimum awareness was calculated. For this calculation an alfa of 0.05 with a two-sided interval and a distance from proportion to limit of 0.1 was used with the expected proportion of 90 %. This leads to a minimum sample size of 35.

To ensure inclusion of data from the different participating countries, this study aims at collecting responses from physicians covering roughly 10 % of purchasing pharmacies that have received InductOs in the past 2 years in each target country. This brings the total to 55 completed surveys which is above the calculated minimum sample size. Taking into account response rate of roughly 60 % and screening failures an estimated 120 surgeons will be screened for eligibility.

#### 4.9 Data analysis

The study population will include all physicians who are screened, are eligible for this study, and completed the questionnaire. All statistical summaries in this study will be descriptive. Frequencies and percentages, with 95 % confidence intervals (CIs) where appropriate, will be presented. Country specific data will be presented. Additional exploratory analyses and sensitivity analyses may be conducted to identify difference between groups of responders.

The primary analysis is aimed at evaluating the proportion of physicians that is aware of the risk of heterotopic ossification and measures described in the educational materials to minimize that risk. A respondent is considered to be aware if they answer 75 % of the questions with regards to heterotopic ossification and the applicable minimization measures correctly. The aRMM will be considered effective if 80 % of the respondents are aware of the described risk of heterotopic ossification and the appropriate measures to minimize them.

The secondary analysis is aimed at identifying the source of physician knowledge. Based on the received data it will be determined to what extent the educational materials are used and are considered an important source of information for the respondents.

#### Milestones:

- Start of data collection: September 2020

- End of data collection: November 2020

- Registration in the EU PAS register of the approved protocol: September 2020

- Final report of study results: December 2020

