#### 9.3 Variables

Information is collected on three main categories, details are described below. The first category is used to describe the population and includes variables around demographics, type of practice, and level of experience in using InductOs. The second category of variables is aimed at measuring the awareness on the risk of heterotopic ossification, the educational materials and knowledge about safe use of InductOs presented in the educational materials. The third set of variables covers the different sources where information on the key messages in the educational materials could have been obtained. A transcription of the intended survey is included in Annex 3.

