## 9.7 Data analysis

The study population will include all physicians who are screened, are eligible for this study, and completed the questionnaire. All statistical summaries in this study will be descriptive. Frequencies and percentages, with 95 % confidence intervals (CIs) where appropriate, will be presented. Country specific data will be presented. Additional exploratory analyses and sensitivity analyses may be conducted to identify difference between groups of responders.

The primary analysis is aimed at evaluating the proportion of physicians that is aware of the risk of heterotopic ossification and measures described in the educational materials to minimize that risk. A respondent is considered to be aware if they answer 75 % of the questions with regards to heterotopic ossification and the applicable minimization measures correctly. In the questionnaire there are 12 (sub)questions raised on the occurrence of heterotopic ossification and the related risk minimization measures. Hence a surgeon needs to answer 9 of these correct to be considered aware. In Annex 3 the (sub)questions included in the scoring of awareness are marked. The aRMM will be considered effective if 80 % of the respondents are aware of the described risk of heterotopic ossification and the appropriate measures to minimize them. With the targeted 55 respondents, this means 44 or more need to be aware.

The secondary analysis is aimed at identifying the source of physician knowledge. Based on the received data it will be determined to what extent the educational materials are used and are considered an important source of information for the respondents.

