# 12. Plans for disseminating and communicating study results

The final study report will be published via the EU PAS register and provided to the EMA and to the local Competent Authorities as relevant.

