## Questionnaire on InductOs

How many years have you been using InductOs?

- $(1) \le 5$  years
- (2) 6-10 years
- $(3) \ge 10$  years
- (4) Prefer not to answer

When was the last time you implanted InductOs?

- (1) 0 <3 months ago
- (2) 3 <6 months ago
- (3) 6 <9 months ago
- (4) 9 < 12 months ago
- (5) 12 24 months ago
- (6) I don't remember

Approximately how many patients have you implanted with InductOs in the past 2 years?

- (1) < 5
- (2) 5 < 10
- (3) 10-<15
- (4) 15-<20
- (5) > 20
- (6) I don't know

Please indicate in percentages how much of your time is spent in the following approaches during your procedures with InductOs. Must sum to 100%.

- (1) Anterior Lumbar Interbody Fusion (ALIF)
- (2) Posterior Lumbar Interbody Fusion (PLIF)
- (3) Transforaminal Lumbar Interbody Fusion (TLIF)
- (4) Oblique Lateral Interbody Fusion (OLIF) / eXtreme Lateral Interbody Fusion (XLIF)
- (5) Posterolateral Fusion (PLF)
- (6) Others (textbox)

When using InductOs in lumbar interbody spine fusion, how much rhBMP-2 do you usually implant in one intervertebral space?

- 1- Less than 4 mg
- 2- Between 4 mg and 8 mg
- 3- Between 8 mg and 12 mg
- 4- More than 12 mg

What best describes your use of the following tools, provided to physicians, when considering the use of InductOs or administering InductOs to a patient?

Tool	Never use	Sometimes use	Frequently use	Always use
Summary of				
Product				
characteristics /				
Package insert				
Educational				
materials				
Other				
information				
provided by the				
Market				
Authorisation				
Holder				
Information				
from peers				
Scientific				
publications				

Would you consider that the available information on the use and administration of InductOs is easy to access?

Y/N

(Note: for the questions below the following legend applies:

- Green text indicates a correct answer
- Orange text indicates a (sub)question which is considered for assessing awareness)

Which of the following are common adverse reactions you associate with InductOs when administering InductOs during lumbar interbody fusion?

1		37 / NT
1-	Urinary retention	Y / N
2-	Fluid collection, like localised edema or (pseudo)cyst	Y/N
3-	Malignancies	Y/N
4-	Neuralgia	Y / N
5-	Osteolysis / increased bone resorption	Y/N
6-	Pseudarthorsis	Y / N
7-	Radiculopathic complaints (radiculitis, radicular pain, radiating	Y / N
	pain, sciatica)	
8-	Heterotopic / ectopic ossification / additional bone growth	Y/N
9-	Back pain	Y / N
10-	Infections	Y / N

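### The protocol due for registration in the month data collection starts carries the marked answer key in Annex 3, and no unmarked version is planned while the survey is open

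*Protocol*

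**What the plan says.** The milestone list in the Protocol's section 4, repeated as a table in section 6, gives "Registration in the EU PAS register of the approved protocol: September 2020" alongside "Start of data collection: September 2020" and "End of data collection: November 2020". All dates are given by month only.

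The questionnaire belongs to that protocol. Section 9.3 says "A transcription of the intended survey is included in Annex 3", and section 9.7 says "In Annex 3 the (sub)questions included in the scoring of awareness are marked". The legend in Annex 3 reads "Green text indicates a correct answer" and "Orange text indicates a (sub)question which is considered for assessing awareness". Annex 1, which lists the stand-alone documents, names only the Product Information report, so the key is not held as a separate file.

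On public posting, section 12 says "The final study report will be published via the EU PAS register". It says nothing about the display of the protocol itself.

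Section 9.7 sets the primary analysis: a surgeon counts as aware with 9 of 12 scored (sub)questions correct, and the measures count as effective if 44 or more of 55 respondents are aware. Under section 9.2 the survey is reached through a personal emailed link, with reminders after 2 and 5 days.

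**The concern.** The primary endpoint is a pass mark on a test. The same document holds the test, the correct answers and the list of items that count, and it is scheduled to enter a register in the month testing begins. The protocol describes no supervision while the survey is completed, and the reminder schedule implies that a respondent may hold the link for several days.

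A respondent who found the marked annex could pass without the knowledge the study is meant to measure, and none of the planned quality checks in section 9.8 would show it. Section 9.10 already treats artificially high awareness as a threat, through self-selection, and section 9.8 randomises the answer options. Neither section considers that the answers might be available. If the result is positive, an assessor could raise this as an objection, and the sponsor would have no data with which to answer it.

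**Working it through.** **Dates and content side by side**

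1. Registration of the approved protocol: September 2020 (sections 4 and 6).
2. Data collection: September to November 2020 (same lists). With month-only dates, registration falls before or early in the collection window.
3. Content of the document to be registered: questionnaire, correct answers and scored items (Annex 3 legend, section 9.7).
4. Provision for an unmarked annex, a withheld annex or delayed display: none found in sections 6, 9.4, 9.6, 9.8, 9.10 or 12, or in Annex 1.
5. Statement of when or how the register shows the protocol: none.

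Items 1 to 4 establish the gap. Item 5 means that public exposure is possible but not shown.

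**The plan's own thresholds**

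- Respondent level: 0.75 × 12 = 9, as stated.
- Planned respondents: 15 + 15 + 15 + 10 = 55, as stated.
- Study level: 0.80 × 55 = 44, as stated.

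**What one respondent is worth**

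The endpoint is a threshold. A surgeon who would score 9 or more anyway adds nothing by reaching 12. A surgeon who would score below 9 and passes because of the key adds 1/55 = 1.8 percentage points.

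Averaged over all who might find the key, the shift per finder is (1 − p) × 1.8 points, where p is true awareness:
- p = 0.90 (the expected proportion in section 9.5): 0.10 × 1.8 = 0.18 points.
- p = 0.75 (assumed): 0.25 × 1.8 = 0.45 points.

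**Illustration of the effect on the success rule**

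Let c be the share of otherwise unaware respondents who pass because they saw the key. Observed awareness becomes p + c(1 − p), and the chance of meeting the rule is P(X ≥ 44) for X ~ Binomial(55, p + c(1 − p)). The values of c, and of p other than 0.90, are assumptions; the protocol gives no basis for c.

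| True awareness p | c = 0 | c = 5 % | c = 10 % | c = 20 % |
|---|---|---|---|---|
| 70 % | 0.067 | 0.103 | 0.154 | 0.303 |
| 75 % | 0.246 | 0.318 | 0.400 | 0.580 |
| 80 % | 0.580 | 0.652 | 0.721 | 0.840 |
| 90 % | 0.993 | 0.995 | 0.997 | 0.999 |

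As a guide to scale, at p = 70 % the expected number unaware is 0.30 × 55 = 16.5, so c = 10 % means 1.65 respondents and c = 20 % means 3.3. At the protocol's expected 90 % the effect is negligible. It matters only if true awareness is below the 80 % bar, which is where a false conclusion of effectiveness is possible.

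**The case against.** A reader might infer that the key is in fact exposed throughout fieldwork. The protocol does not support that. It names the register as a publication channel for the final report only, says nothing about whether annexes are shown with the registered protocol, and gives months rather than days, so registration could follow the first responses. This objection stands, and it limits the point to a risk.

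A reader might also infer that every surgeon who finds the key moves the result by 1.8 points. That is wrong for anyone who would have passed anyway, as shown above.

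Two further arguments have weight. First, section 7 says that the educational materials add nothing to the SmPC and can be reached through a dedicated website, so a respondent to this survey could already look up much of the content. What the key adds is the exact scored items with the answers marked, which removes the need to search or understand. Second, nothing directs surgeons to the register: they are screened by telephone and sent a personal link. Few would look.

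Finally, registering a protocol with its scoring fixed makes the prespecification openly checkable, which has value. That value is kept if a dated keyed version is held by the regulator and posted afterwards.

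**Conclusion.** The point holds as a low-severity, cheap improvement. The protocol schedules registration of a document that contains the marked key for the month data collection starts, and it provides no unmarked or withheld version before collection ends in November 2020. The key to an online test with no described supervision may therefore be public during fieldwork.

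The size of any effect cannot be determined from the protocol. It depends on whether and when the register shows the marked annex, and on how many surgeons below the pass mark would find and use it, a number that is probably small. The illustrative probabilities rest on assumed values and are not an estimate of bias. The case for acting is that this route to inflated scores is avoidable and could not be detected afterwards, and that closing it costs very little.

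**What to change.** - Register the protocol with Annex 3 unmarked, with neither green nor orange text.
- Add the keyed questionnaire to Annex 1 as a dated stand-alone document, supply it to the regulator before data collection starts, and change the cross-reference in section 9.7 to point to it.
- State in section 6 or section 12 that the keyed version will be posted after data collection has actually closed, at the latest with the final report.

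Design, sample, scoring and timelines are unchanged. The cost is one extra file and a second upload. The drawback is that the scoring key becomes public about three months later (September to December 2020), although it stays fixed and dated in the regulator's copy.

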# 5. Amendments and updates

None after the start of data collection.

## 6. Milestones

Milestone	Planned date
Start of data collection	September 2020
End of data collection	November 2020
Registration in the EU PAS register of the approved protocol	September 2020
Final report of study results	December 2020

# 7. Rationale and background

The active ingredient of InductOs is dibotermin alfa or recombinant human Bone Morphogenetic Protein 2. Its osteoinductive properties result in the induction of new bone tissue at the site of implantation.

InductOs is approved for:

- single-level lumbar interbody spine fusion as a substitute for autogenous bone graft in adults with degenerative disc disease who have had at least 6 months of non-operative treatment for this condition.
- treatment of acute tibia fractures in adults, as an adjunct to standard care using open fracture reduction and intramedullary unreamed nail fixation.

Instructions for proper preparation and administration of dibotermin alfa/ACS are provided in the Summary of Product Characteristics (SmPC) and instructions for reconstitution are provided in the labelling of the pack. The aforementioned instructions consist of routine measures to minimise important identified (heterotopic ossification, osteolysis/resorption bone increased, fluid collection) and potential risks (medication errors and incorrect use, malignancies, antibody formation) by providing information on the measures to take during administration of dibotermin alfa/ACS or situations to avoid.

Additional risk minimisation measures (aRMM) to increase awareness about the identified risk of heterotopic ossification (especially in posterior surgical approaches for lumbar interbody fusion) and the potential risk of medication errors and misuse are available in the form of educational materials. These educational materials also aim at providing guidance on how to manage these risks. The aRMM present the information from the Summary of

Product Characteristics (SmPC) supported with visual aids, e.g. a demonstration of the correct preparation technique. The aRMM and related educational materials contain no information which is not contained in the SmPC.

InductOs educational materials consist of a preparation guide, two videos (one for each indication), and the SmPC. The educational materials can be accessed through a dedicated website, or upon request to the MAH.

The results from measuring the educational materials effectiveness as described in the Risk Management Plan (RMP), were considered suboptimal by the Pharmacovigilance Risk Assessment Committee (PRAC) in view of the context of administration and availability of data. An assessment of outcome indicators, i.e. the occurrence of heterotopic ossification and medication errors and misuse using the available data sources in the EU, was deemed unfeasible. The PRAC agreed that the effectiveness evaluation could be based exclusively on careful interpretation of data on newly chosen process indicators. Specifically, Medtronic BioPharma considered the use of a survey to determine the available knowledge of physicians administering InductOs. Therefore, Medtronic BioPharma is conducting this cross-sectional knowledge check with the aim of obtaining a better understanding of the knowledge of the physicians regarding the risks and minimisation instructions that are described in the educational materials.

